## **Study Visit 3 (Overnight Sleep Study) (within 4 to 6 weeks of visit 2)**

Participants will be asked to come to the sleep lab at a scheduled date and time. The sleep testing will begin near the subject's usual bedtime and ends at approximately 6 A.M.

Prior to the sleep study with the therapy device, the trained technologists will verify mask size, fit, and adjustment. The sleep test will involve using the device the participant has been receiving therapy from in the initial 4 to 6 weeks. Details of the PSG set up can be found in the standard procedures section of the protocol.

Morning ABG, Therapy Comfort and HRQL assessments: Following the completion of the sleep study (morning after), all participants will return to the research center where their activity monitors will be downloaded, fill out study-related questionnaires as well as have their ABGs collected. Details on ABG collection and study questionnaires can be found in the standard procedure section of the protocol. Participants in Cohort 1 that were randomized to their current NIV device for the initial 6 weeks will now be asked to use the Vector device for the next 6 weeks. The Vector device will be set up with the

Device settings determined during the titration procedure at study visit 2.

## **Study Visit 4 (Overnight Sleep Study - within 4 to 6 weeks of visit 3)**

Participants will be asked to report to the sleep lab for the second overnight sleep study at a scheduled date and time. The sleep testing will begin near the subject's usual bedtime and end at approximately 6 A.M.

Prior to the sleep study with the therapy device, the trained technologists will verify mask size, fit, and adjustment that was determined at study visit 1. Details of the PSG set up can be found in the standard procedures section of the protocol.

Morning ABG, Therapy Comfort and QOL assessments: Following the completion of the sleep study (morning after), all participants will have to return to the research center where their activity monitors will be downloaded, fill out study related questionnaires as well as have their ABGs collected. Details on ABG collection and study questionnaires can be found in the standard procedures section of the protocol.

In the event that participants are unable to come into the research clinic for visit 3 or 4, remote administration of questionnaires via telephone or direct mail may be conducted. Participants may be asked to return their device SD cards via direct mail using a provided postage-paid envelope.

Procedures														
	Determine eligibility	Enrollment/Baseline		Visit 1 (day 0)		Visit 2 Daytime Titration		Week 1: Daily Check-in Calls		Weeks 2-6: Weekly Check-in Calls	Week 4: Diary Reminder Call 1	Visit 3 Overnight PSG study	Week 1: Daily Check-in Calls	Week 4: Diary Reminder Call 2
Chart Review	X													
Informed consent		X												
H&P , demographics		X												
QoL Questionnaires			X							X			X	
EFL assessment	X													
Morning ABG										X			X	
In Lab Sleep Study (PSG)										X			X	
Device titration (NIV Current)			X											
Device Titration (NIV Naïve)		X	X											
Clinical follow up (assess patients concerns/issues with device, mask, or other)										X	X		X	
Actigraphy set up/ data download		X								X			X	
Device data download (NIV Current)										X			X	
Device data download (NIV Naïve)				X										
Sleep Diary Reminder								X			X			
Side effects and AE assessment				X	X	X	X	X	X	X	X	X	X	

## **A. Standard Procedures**

### **Arterial Blood Gas / Room Air SpO2 assessment**

Arterial blood gases and SpO2 should be collected with the participant breathing room air for at least 15 minutes prior. The participant should rest in the seated position for 10 minutes prior to drawing the sample.

### **Quality of Life Questionnaires (QOL)**

Health related quality of life (QOL) measurement is an important tool for measuring health status changes in participants receiving an intervention. The COPD Assessment Test (CAT), St. George Respiratory Questionnaire and Modified Medical Research Council Dyspnea Questionnaire (MMRC) will be used in this study. Participants will be asked to complete these questionnaires at Visits 2-4.

### **PSG's**

During all lab nights, participants will be set-up with a standard PSG montage that will include the following sensors:

- Two RIP belts secured around the chest and abdomen to measure movements associated with breathing effort
- A small sensor which attaches to the chest belt to measure body position
- Lead II ECG electrode derivation
- EEG electrodes attached to the scalp and face to measure sleep stages (including at least C4, C3, A1, A2, O1, O2, GND EEG, Left Outer Canthus (LOC) and Right Outer Canthus (ROC) EOG and submental EMG)
- A flexible finger sensor placed on the finger to measure oxygen saturation (average signaling time of 3 seconds)
- A microphone attached to the skin at the base of the neck to measure snoring sounds
- Surface electrodes attached to the skin bilaterally over the anterior tibialis muscle, to measure leg movements
- Transcutaneous CO2 monitoring

### **Scoring**

All sleep studies will be scored by the qualified site personnel. All sleep variables will be classified and scored using the 2007 AASM criteria additionally, all sleep variables will be scored using a modified Hypopnea rule as defined below.

- Apneas will be scored according to AASM Scoring Manual rules VIII.3.A, B.
- Hypopneas will be scored according to the AASM Scoring Manual rule VIII.4.A for desaturations with a nadir below 90%.

For hypopneas yielding desaturations with a nadir of 90% or greater, a modified rule VIII.4.A will be used that requires an arousal (rule V.1.A) to accompany the event for scoring as a hypopnea.

**NOTE:** If the participant slept less than 3 hours on any lab night, they, may be asked to repeat the overnight sleep test. If the patient is unwilling to repeat the sleep test, furthermore, a replacement participant will then be enrolled.

### **Actigraphy Measurements & Sleep Diary**

Actigraphy is a method of measuring activity and sleep which is achieved by wearing a small watch-like device for an extended period of time. Most units contain an accelerometer and continually record the movement it undergoes. These data are later read to a computer for analysis. These data will provide an objective record of physical activity and sleep / wake patterns throughout the 6 weeks of home use.

The wrist-worn actigraph device will provide a continuous measure of both how much the participant has slept during the night and how active they are during the day. There is an event button that the participant will be asked to press when the participant is in bed, near asleep and also upon awaking.

Participants may be asked to keep a sleep diary during the last two weeks of each arm of the study in order to supplement the actiwatch data. The study team will call the participant to remind them to start using the diary.

### **VI. Selection and Withdrawal of Subjects:**

#### **Inclusion Criteria**

1. Age  $\geq$  40 years of age;  $\leq$  80 years of age
2. Ability to provide consent
3. COPD patients with hypercapnia (as defined as  $\geq$  52mmHg) who are either current NIV users or naïve to NIV
4. On average, use NIV more than 4 hours per night (Current NIV users).
5. Must present with EFL via screening of the Vector device at 3 cmH2O
6. Have an EPAP to abolish EFL greater or equal to 6cmH2O

#### **Exclusion Criteria:**

1. Any major non-COPD uncontrolled disease or condition, such as congestive heart failure, malignancy, liver or renal insufficiency (that requires current evaluation for liver or renal transplantation or dialysis), amyotrophic lateral sclerosis, or severe stroke, or other condition as deemed appropriate by investigator as determined by review of medical history and / or participant reported medical history
2. Suffering from a COPD exacerbation (Defined as hospital admission, ER/urgent care visit, MD visit with medication change or other intervention deemed to be

clinically significant by the investigator at the time of data collection or in the 14 days prior to data collection

3. Self-reported Pregnancy or positive pregnancy test for women of childbearing potential.
4. Employee or family member that is affiliated with Philips
5. Currently employed by a manufacturer of respiratory products or family member employed by a manufacturer of respiratory products
6. Any history of giant bulla (size >1/3 hemi-thorax)
7. History of pneumothorax ≤ 6 months
8. Participants currently using a PAP or NIV device at home with a documented EPAP setting on their current device that is greater than the calculated EPAP determined during the therapy session of the screening visit (Current NIV Users).
9. Life expectancy ≤12 months as determined by clinical investigator
10. Low BP: Systolic <90
11. Recent cranial surgery (i.e, less than 1 year)
12. Impaired swallowing as reported by participant or diagnostic exam
13. Recent upper airway or GI surgery within the past 6 months
14. Unable to be fitted with mask
15. Excessive secretions as reported by clinical investigator/physician assessment, inability to maintain a patent airway or adequately clear secretions, or at risk for aspiration of gastric contents
16. Diagnosed with acute sinusitis or otitis media
17. Epistaxis, causing pulmonary aspiration of blood
18. Existing respiratory failure
19. Participants who are naïve to NIV (Cohort 2) that use the device fewer than 3 out of 7 nights during the second week of the 2-week acclimation period
20. Participants who are naïve to NIV (Cohort 2) that average less than 4 hours of device use during the second week of the 2-week acclimation period
21. Participants who are naïve to NIV (Cohort 2) with an average nightly 90% EPAP pressure during the second week of the 2-week acclimation period that is higher than the titrated EFL EPAP pressure determined at the screening visit.

### **Withdrawal:**

The term “discontinuation” refers to the participant’s premature withdrawal from the study prior to completing all procedures. Participants may be discontinued from the study for any of the following reasons:

- If in the investigator’s judgement, continuation in the study may prove harmful to the participant. Such a decision may be precipitated by adverse events, including fever, nausea, rash, changes in vital signs, or the development of a new medical

condition. The investigator will be solely responsible for making medical/safety decisions regarding the participant's continued participation in the study.

- Noncompliance;
- At the request of the participant.
- Further admission with AECOPD as the primary diagnosis

The study team will document whether or not each participant completed the study. If, for any participant, study treatment or assessments were discontinued, the reason will be recorded.

For the naïve NIV patient cohort, participants will be allowed to keep the device until a marketed device can be provided to them through normal commercial distribution pathways.

The study goal is to have 30 participants successfully complete the study. It is estimated that 50 patients may need to be enrolled in order to complete 30

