### Secondary Objectives:

- To evaluate treatment effect of Vector on overall quality of life
- To evaluate treatment effect of Vector on sleep quality
- To evaluate treatment effect of Vector on physical activity levels
- To Evaluate treatment effect of Vector on Ventilator collected parameters
- To Evaluate treatment effect differences on nocturnal SpO2 and PaCO2 or TcCO2

**Endpoints:**Primary Endpoint:

Daytime CO2 levels at the end of 4-6 weeks of therapy as determined by Arterial Blood Gas (PaCO2)

Secondary Endpoints:

- Average daily device usage
- Therapy Comfort and Preference
- Incidence of Unanticipated Serious Adverse Device Effects (USADEs) and Serious Adverse Events (SAEs) for the Vector vs. the control group.

Exploratory Endpoints:

- Changes in quality of life scores ((CAT) SGRQ, dyspnea ratings mMRC),
- Ventilator collected parameter differences after 6 weeks of use (Respiratory Rate (RR), Minute Ventilation (MV))
- Sleep Quality differences as measured by PSG and actigraphy
- Changes in activity levels (mean and max activity counts)

**Study Population:** Approximately 30 COPD patients with chronic hypercapnia and evidence of expiratory flow limitation will be included.  
**Phase:** Pilot study

**Sites/Facilities Enrolling Participants:** Temple University Hospital

**Description of Study Intervention:** NIV with Auto Adjusting EPAP

**Study Duration:** Approximately 12 months

**Participant Duration:** Approximately 15 weeks

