###### **Study Hypothesis:**

We hypothesize in patients with hypercapnic COPD, NIV therapy provided by the Vector device, with an optimized automatically adjusting EPAP to abolish expiratory flow

limitation, will maintain equal levels of gas exchange (PaCO2) will provide patients with improved therapy comfort and adherence when compared to standard NIV.

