### **Secondary Endpoints:**

1. Average 30-day Ventilator Usage hours
2. Patient Comfort and Therapy Preference based questionnaire responses

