### **Phone Follow-ups:**

Participants will be sent home with the Vector device with their randomized therapy. During the initial week, the participant will be contacted daily to determine if there are any problems with the device and to encourage compliance. Participants will be asked to use the Vector device at night for the following 6 weeks. Participants will then be contacted weekly from week 2 to the last week of their take home period (maximum of 6 weeks). During the second take home period, all participants will be called daily during the first week only.

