## **VIII. Assessment of Performance**

Device performance will be based on the following patient physiological and device recorded parameters:

- Daytime PaCO2 levels after 30-day period, method (Visits 3 and 4)
- Nocturnal TCO2 levels during sleep study (Visits 3 and 4)
- Nocturnal SpO2 levels during sleep study (Visits 3 and 4)
- Ventilator collected parameters over the 30-day use period (RR, MV, usage hours) (Visits 3 and 4)

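### After randomisation, undefined noncompliance can end study participation although device use is a compared endpoint, and the 30-day usage window does not fit a 28-night period

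*Combined protocol and SAP*

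**What the plan says.** In the Withdrawal part of section VI, discontinuation means "premature withdrawal from the study prior to completing all procedures", so it is departure from the study and not merely from the device. The list opens with "Participants may be discontinued from the study for any of the following reasons", and one entry is the single word "Noncompliance". It has no threshold, object or time limit.

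The numeric use rules all act before randomisation: more than 4 h per night for current users (Inclusion Criteria), and the acclimation rules for the naïve cohort (Study Visit 2; Exclusion Criteria 19 and 20). Under Phone Follow-ups, after randomisation, staff call participants at home "to determine if there are any problems with the device and to encourage compliance".

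Device use is a compared outcome. The Study Hypothesis expects "improved therapy comfort and adherence when compared to standard NIV". The Secondary Endpoints in section IV list "Average 30-day Ventilator Usage hours", and the Synopsis lists "Average daily device usage". Section VIII also uses a 30-day period, assessed at Visits 3 and 4. Sections V, Visit 3 and Visit 4 set each period at 4 to 6 weeks.

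Section XI compares the therapies as pairs, foresees no imputation and rules out sensitivity analysis. It names everyone who consented as the set for the primary analysis and requires a listing of reasons for discontinuation. It adds that the results may be used to power a pivotal trial.

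**The concern.** If noncompliance means low device use, the value of an outcome decides whether the rest of that outcome is collected. The realistic case is low use in the first period, seen at Visit 3, where the schedule table (partly broken in the text available) appears to place an on-treatment download. Ending participation there means no second period, no Visit 4 blood gas, and no usage or PaCO2 pair. An analysis set of everyone who consented cannot supply a period that was never collected, and listing the reason shows the loss without repairing it.

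At stake are the number of pairs, their balance between sequences, and the usage level, SD and dropout rate that a pivotal trial might take from this pilot.

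The window is a separate fault in the same endpoint. A 28-night period cannot hold 30 nights, and in a longer one the text does not say which 30 count.

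**Working it through.** **The plan's own figure.** The only planning number is 50 enrolled for 30 completers, an implied loss of 1 − 30/50 = 40%. No reasons are apportioned, so it does not show how much noncompliance contributes.

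**Lost pairs: inputs.** The documents give no usage mean, SD or correlation; all of the following are assumed.
- Mean 5.5 h per night on SOC before selection, SD 2 h, correlation 0.6 between periods.
- Only people with at least 4 h before randomisation are kept, echoing the entry rules.
- 1:1 sequence; the pair is lost if period-1 use falls below a cut-off of 2, 3 or 4 h, applied automatically and alike under both therapies.
- True difference (Vector minus SOC) of −0.75, 0 or +0.75 h.

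**Model.** Usage in each period = mean + person effect + period noise, with on-treatment values floored at 0. SD of the paired difference = √(2 × 2² × (1 − 0.6)) = 1.79 h. SE for 30 pairs = 1.79/√30 = 0.33 h.

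**Simulated results.**

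| True difference | Cut-off | Difference in kept pairs | Pairs lost | Rise in Vector mean |
|---|---|---|---|---|
| +0.75 h | 2 h | 0.74 h | 0.9% | 0.02 h |
| +0.75 h | 3 h | 0.72 h | 3.5% | 0.09 h |
| +0.75 h | 4 h | 0.70 h | 10.4% | 0.24 h |
| −0.75 h | 2 h | −0.73 h | 2.5% | 0.09 h |
| −0.75 h | 3 h | −0.71 h | 8.1% | 0.23 h |
| −0.75 h | 4 h | −0.70 h | 19.9% | 0.49 h |

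- With no true difference, the kept pairs give 0.
- The shift is 0.01 to 0.05 h in either direction. The largest, 0.05 h, is about 0.16 of the SE.
- Loss by sequence at the 4 h cut-off, true −0.75 h: 25.6% Vector first, 14.1% SOC first. For +0.75 h, SOC first is again 14.1%, so Vector first is 2 × 10.4 − 14.1 = 6.7%. The sequence that starts with the less-used therapy loses more.
- For −0.75 h, the SD of the difference falls from 1.79 to 1.76, 1.74 and 1.73 h.
- If only half of low users are removed, true −0.75 h: about 1.3%, 4% and 10% of pairs lost, shift about 0.01 to 0.02 h.
- Wider grid (mean 5 to 6.5 h, SD 1.5 to 2.5 h, correlation 0.4 to 0.8, both signs, automatic removal): shift 0 to 0.07 h (0 to 0.24 SE), pairs lost 0 to 31%.

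The effect on PaCO2 is not sized, because the documents give no relation between use and PaCO2.

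**Window.**
- 4 weeks × 7 = 28 nights, and 30 − 28 = 2 nights too many.
- 6 weeks × 7 = 42 nights. A 30-night window covers 30/42 = 71% and leaves out 12 nights.
- If hours over 28 nights are divided by 30, 6.0 h becomes 6.0 × 28/30 = 5.6 h.
- If 30 days are counted back from Visit 4 in a 28-night second period, 2 nights belong to the other therapy. With a clean first-period window, the contrast becomes (28V + 2S)/30 − S = (28/30)(V − S), so 1.0 h reads as 0.93 h.
- With an assumed linear drift of 0.5 to 1.0 h over 42 nights, first-30 and last-30 averages differ by 12/41 × drift = 0.15 to 0.29 h.
- All-night means over 28 and 42 nights differ by 7/41 × drift = 0.09 to 0.17 h, so averaging over whatever nights exist is not a complete cure when a person's two periods differ in length.

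**The case against.** The rule is permissive, and noncompliance may mean missed visits or procedures. The one passage linking compliance to home use describes encouraging low users, not removing them. Both points stand: the harm is conditional on a reading that the text allows but does not require. What remains is that the text does not exclude that reading after randomisation.

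The shift is one to three minutes a night, towards zero, in a pilot without a power calculation, and enrolling 50 for 30 completers buffers the numbers. This also stands. The buffer protects how many pairs there are, not which people supply them.

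A reader might infer that the plan removes low users, or that the rule manufactures a difference in favour of Vector. The documents set no use threshold after randomisation, and a rule applied alike to both therapies produces nothing when there is no true difference. A reader might also quote only the losses of up to 20%. Those belong to Vector being used less, the opposite of the hypothesis, and to automatic removal.

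A harsher model drops a pair when either period averages under 4 h, with no prior selection on use. Under its own assumed inputs it loses 5 to 38% of pairs, and a true 1.0 h reads as 0.75 to 0.96 h. But low use found at the Visit 4 download comes when second-period usage is already recorded, and the plan does select on use before randomisation, so that is not the realistic case.

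Finally, in a crossover, second-therapy data exist only if that therapy is started. If it is not, a Visit 4 blood gas reflects assignment and not actual use. That limits what data retention can recover, but does not argue against collecting what can be collected.

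**Conclusion.** Both parts hold, in modest form. The Withdrawal section leaves open that a low value of a compared endpoint ends its own collection after randomisation, and the planned analysis cannot recover the lost pair. The treatment difference is barely affected: about 0.01 to 0.05 h towards zero in the mid case and nil without a true difference, provided the rule is applied alike under both therapies. The more visible effects are the lost pairs (about 1 to 10% if Vector is used 0.75 h more, 2.5 to 20% if 0.75 h less, roughly half with half removal), unequal loss by sequence when the therapies differ, and absolute usage that looks better than it was. These matter mainly because the pilot may inform a pivotal design. Every usage input is assumed.

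The window fault needs no assumption: 30 nights exceed a permitted 28-night period by 2, and the choice of nights in longer periods is unstated. The Synopsis wording may give only the unit, so it is not treated as a contradiction. The point merits correction with medium confidence; it does not invalidate the design.

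**What to change.** 1. **Withdrawal section.** State that after randomisation low device use alone is not a reason to stop collecting study data. Device downloads and the Visit 3 and Visit 4 assessments are still sought unless consent is withdrawn or the investigator judges continuation harmful, and data are analysed by the therapy assigned in that period. Decisions on treatment stay as written, and no adherence threshold is proposed.

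2. **Synopsis, Secondary Endpoints and section VIII.** Replace the 30-day window with one definition that fits every permitted period and is the same for both therapies. An example is mean hours per night over the first 28 nights of each period, counting nights without use as zero, with the mean over all assigned nights as a supporting summary.

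The cost is protocol and SAP wording, plus some visits, sleep studies and blood gases in participants with little use. Up to 42 − 28 = 14 nights per period fall outside the main usage figure, which is why the all-nights mean is kept alongside.

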## **XVIII. Risk and Benefit Analysis**

### **A. Potential Risks and Discomforts**

Adverse effects of NPPV are usually minor and manageable. The masks may cause some discomfort and air pressure and flow have adverse effects. All adverse effects encountered, including mask discomfort, nasal or mouth congestion or dryness, eye irritation, gastric insufflation, and nasal bridge ulceration will be recorded on data sheets that are part of the case report form.

The risks of using the Vector NIV Device are minimal. Use with the NPPV devices may cause a decrease in the inability to adequately clear secretions, an increased risk for aspiration of gastric contents, increase in symptoms of sinusitis or otitis media, and decrease in blood pressure. These are minimal risks of using the device and should they occur during the course of the study, they be recorded. Other more serious adverse effects, such as pneumothorax or aspiration pneumonia, are distinctly unusual

in the outpatient setting, but will be recorded if they occur. Significant adverse events will be reported to the Institutional Review Board. Patients currently on NIV may find Vector to be less comfortable than their previous NIV, but this is not a real medical risk.

Arterial blood gas determinations are part and parcel of routine pulmonary function testing and are performed by trained respiratory therapists on a daily basis. The blood gas draws as part of this study is consistent with usual care in initiating NIV. The research technician will employ the usual precautions while performing such a procedure by employing adequate aseptic technique. The arterial blood gas sampling test can cause pain, tenderness or swelling at the puncture site and possibly bleeding, local infection, lightheadedness or fainting.

Standard PSG (sleep study) risks might include: complaints of skin irritation from the adhesives or tapes used to secure the electrodes and any necessary skin preparation.

Participants may also find some of the chemical adhesive smells offensive. The participant may sleep poorly.

The patient may sleep poorly during the nocturnal sleep study and thus may be sleepy the next day. If the patient is too sleepy to drive home, other forms of transportation will be utilized.

COVID-19 is a risk with any in-person activity, but proper mitigation strategies, including COVID-19 screening, disinfection, and other site safety procedures, will be implemented to minimize patient risk.

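### A participant who stops a randomized therapy early has no planned route to a comfort rating, so the paired comfort comparison can lose the people who found a therapy least comfortable

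*Combined protocol and SAP*

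**What the plan says.** The Study Hypothesis states that Vector "will provide patients with improved therapy comfort and adherence when compared to standard NIV". The Secondary Endpoints list "Patient Comfort and Therapy Preference based questionnaire responses". The documents name no comfort scale.

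Comfort is placed at the end of each period. Study Visit 3 has "Morning ABG, Therapy Comfort and HRQL assessments: Following the completion of the sleep study (morning after"), and Study Visit 4 has the equivalent entry. A remote option follows under Study Visit 4: "In the event that participants are unable to come into the research clinic for visit 3 or 4, remote administration of questionnaires" by phone or mail may be used, and SD cards may be mailed back.

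The Withdrawal section defines discontinuation as "premature withdrawal from the study prior to completing all procedures". Participant request and noncompliance are among the listed grounds. If treatment or assessments stop, the reason is recorded. No questionnaire at stopping is described.

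Under Primary Analysis, endpoints are compared as paired samples. Missing Data anticipates no imputation, and General Considerations rules out sensitivity analysis.

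**The concern.** Discomfort is a plausible reason for giving up a ventilator at home, and giving it up removes the rating that would show the discomfort. Missingness would then depend on the outcome itself, for an endpoint on which the trial hopes to show a benefit.

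The protocol recognises the possibility. Potential Risks and Discomforts says "Patients currently on NIV may find Vector to be less comfortable than their previous NIV, but this is not a real medical risk". A comparison restricted to people who finished both periods describes those who tolerated both therapies well enough to finish. That may differ from the comparison among everyone randomized.

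The stake is wider than one secondary result. Determination of Sample Size says the pilot may inform a larger pivotal trial, and the registration section says the data may support regulatory clearance. A rating not collected at stopping cannot be recovered at analysis.

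**Working it through.** **Step 1. What each participant can contribute under the written schedule.**

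- Completes both periods: comfort at Visits 3 and 4, so one pair.
- Stops in period 1 and leaves: no comfort rating and no pair.
- Stops in period 2 and leaves: at most the Visit 3 rating and no pair, although both therapies have been tried.

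**Step 2. Whether another contact fills the gap.**

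- Phone Follow-ups: in the first week participants are "contacted daily to determine if there are any problems with the device and to encourage compliance"; no comfort rating is named.
- Visit 1 experience questions: these follow the short screening and titration sessions, before randomization.
- Borg rating in Appendix A: it selects a titration setting and does not rate a period of home use.
- Remote questionnaires: tied to being unable to attend Visit 3 or 4, and not extended to early stoppers.
- Adverse effects, including mask discomfort: recorded and put in listings, but not part of the comfort comparison.

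None supplies a comfort rating for an early stopper. General Considerations says the primary analysis includes all consented participants, but a paired test without imputation cannot use someone who has no pair.

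**Step 3. How many participants.** The Withdrawal section gives about 50 enrolled for 30 completers: 1 - 30/50 = 40%, or 20 people. That total probably includes failures at EFL screening or acclimation, before randomization. The number stopping a randomized therapy is therefore unknown, between 0 and 20, and those stopping for discomfort are a subset.

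**Step 4. Mean comfort, illustration only.** Every input is assumed: a 0-10 scale, means 5 (Vector, V) and 6 (SOC, S), SD 2 on each, correlation 0.5, bivariate normal. A participant leaves if either rating falls below a cut c. The completers' difference is E[V - S | V > c, S > c], against a true -1.0.

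- SD of the difference = √(2² + 2² - 2 × 0.5 × 2 × 2) = 2. With 30 pairs the standard error is 2/√30 = 0.37.
- c = 2: 8.1% leave and the difference is -0.91. The shift is 0.09, and 0.09/0.37 = 0.24 standard errors.
- c = 3: 19.3% leave and the difference is -0.84. The shift is 0.16, and 0.16/0.37 = 0.43 standard errors.
- The share rating Vector higher moves only from 31% to 32%.

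With the two means exchanged, the same rule turns a true +1.0 into +0.91 or +0.84. The comparison shrinks against whichever therapy is more comfortable.

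**Step 5. Preference, illustration only.** Suppose 21 of 30 completers prefer Vector: 70%, exact two-sided binomial p = 0.043. Count s further participants who stopped Vector for discomfort as not preferring it, and assume nobody stopped SOC.

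- s = 2: 21/32 = 66%, p = 0.11.
- s = 5: 21/35 = 60%, p = 0.31.

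A near-threshold result is thus sensitive to a few stoppers, but only because all of them were assigned to one therapy and one answer.

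**The case against.** Several points on the other side are sound.

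- The Withdrawal section says participants *may* be discontinued and mentions stopping treatment or assessments. Someone who stops the device could still attend Visit 3 or 4. A reader might infer that early stoppers can never contribute; the text does not say that. It neither bars nor arranges it.
- Intolerance is not invisible. Adverse effects, including mask discomfort, are recorded, and reasons for discontinuation are listed under Participant Disposition. A count of discomfort stops is largely obtainable already; a comfort rating is not.
- A reader might take the risk section as a forecast that Vector will be less comfortable. It says only that current users may find it so.
- Entry rules reduce dropout: current users must average more than 4 hours of NIV per night, and naïve participants must pass an acclimation period. This stands in part. Both filters test tolerance of standard NIV, since Vector therapy is switched off during acclimation, so neither tests tolerance of Vector.
- A rating after full exposure is a defensible choice, and a rating in week 2 measures something different. That is a reason to keep early ratings separate, though not to omit them.
- This is one secondary endpoint in a pilot without a power calculation, and the modelled shift is small beside sampling error.

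**Conclusion.** The gap is real. The protocol provides no route by which a participant who stops a randomized therapy early gives a comfort rating, and the paired analysis then leaves that participant out. If discomfort drives stopping, the worst ratings of the less tolerable therapy are the ones lost.

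The documents do not allow the size or direction of the bias to be computed. Under one assumed model it is 0.09 to 0.16 points on a true difference of -1.0, less than half a standard error with 30 pairs.

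Two stronger readings are tempting. One is that the loss favours Vector. That holds only if Vector is the less tolerable therapy; if SOC is, the loss works against Vector. The other is that preference for Vector must be materially inflated. The model in Step 4 moves the share rating Vector higher by about one percentage point. Larger shifts, as in Step 5, need the added assumptions that all stoppers stopped Vector and would not prefer it.

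The point is a cheap improvement to a secondary endpoint and does not call the design into question.

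**What to change.** In the Withdrawal section, distinguish stopping a therapy from leaving the study. Unless consent is withdrawn, when a therapy is stopped early:

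- give the same comfort questionnaire as at Visits 3 and 4, soon after stopping;
- ask the preference question if both therapies have been tried;
- retrieve the SD card.

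Extend the phone and mail route under Study Visit 4 to these participants. Beside the paired comfort and preference results, report how many stopped each therapy for discomfort, by therapy and period, with their early ratings on a separate line.

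This concerns data collection only and leaves unchanged when or why anyone stops treatment. The cost is a wording change plus a phone call and a postage-paid envelope per early stopper. The downside is that early ratings reflect shorter exposure, so they should not be pooled with the end-of-period ratings.
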